COVER PAGE

Official title of the study: Efficacy of Gluma desensitizer in controlling the immediate post treatment sensitivity in etch-and-rinse and self-etch adhesive occlusal composite restorations

NCT04248803

Date of the document: 02-09-2025

Efficacy of Gluma desensitizer in controlling the immediate post treatment sensitivity in etch-and-rinse and self-etch adhesive occlusal composite restorations

NCT04248803

BRIEF SUMMARY

Background

One of the most widely used esthetic restorations in dentistry is composite. Despite the indispensable value that composite brings to a dentist's arsenal, the postoperative sensitivity following composite resin restorations are an undesirable outcome often leading to patient discomfort.

GLUMA desensitizer, a solution containing glutaraldehyde and hydroxyethyl methacrylate (HEMA), is widely used to reduce sensitivity by occluding dentinal tubules and stabilizing collagen fibrils. However, the ideal timing of GLUMA application in different adhesive protocols remains uncertain, raising questions about its effect on postoperative sensitivity, adhesive bond strength, and long-term restoration success.

This clinical trial aims to evaluate the effectiveness of GLUMA in controlling the immediate post treatment sensitivity following occlusal composite restorations. In addition, to compare the difference between the bonding systems (Etch-and-rinse & Self-etch) on reduction of post restoration sensitivity with or without Gluma desensitizer.

Sample Size, Blinding and Randomization

For this clinical trial, a sample size of 504 restorations was calculated to be sufficient for detecting statistical difference using G* power software (α probability error – 0.05 and effect size – 0.2).

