In this single-blinded clinical trial, the numbers of arms were randomly assigned to six groups. The participants of the study were informed about the trial but were unaware of which treatment group they were allocated to. The clinician and researcher were aware of the groups and treatments given. All patients were allocated using Block randomization. It works by dividing participants into individual blocks and then randomly assigning treatments within each block, ensuring roughly equal numbers in each group within that block. In this clinical trial, a block size of 6 (1, 2, 3, 4, 5, 6) was employed for equal enrolment. The prepared blocks were printed in sheets and patients who met the eligibility criteria were systematically assigned in a continuous fashion. After every 6th patient, the enrolment would continue on to the next block from 1.

Arms (n=84 in each)

Arm 1: Total Etch Control group (No desensitizer application)

Arm 2: Total Etch Gluma prior to acid etchant usage

Arm 3: Total Etch Gluma desensitizer application after acid etchant usage

Arm 4: Self Etch Control group (No desensitizer application)

Arm 5: Self Etch Gluma desensitizer application prior to etching

Arm 6: Self Etch Gluma desensitizer application after self-etch adhesive usage

Materials and Methodology

Caries excavation was done using diamond burs (Mani Co., Tochigi, Japan) with water coolant. Cavity extent was until sound hard or firm discolored or non-discolored dentin was achieved. This was cross-checked by an Experienced Post Graduate Supervisor (EPGS) blinded to treatment allocation group. Those teeth with width of the cavity preparation were no more than 1/3rd of the inter-cuspal width were included. Radiographs (Durr PSP Sensor, Durr, Germany) are taken to assess the depth of the

preparation and Remaining Dentin Thickness (RDT). Two RDT measurements from mesial and distal pulp horn to floor of the preparation were calculated. Mean RDT was derived from the two readings. Radiograph assessment was done by EPGS. Teeth were excluded from the study if they had pulp exposure or a prepared cavity that did not meet standardization requirements.

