The Kruskal-Wallis test is a non-parametric statistical test used to determine if there's a significant difference between the medians of three or more independent groups. It's an alternative to the one-way ANOVA when the data doesn't meet the assumptions of normality or equal variances.

STATISTICAL ANALYSIS OVERVIEW:

This present study contains six arms whose descriptions have been provided in the brief summary. The statistical analysis was performed using IBM SPSS version 23. The normality was assessed using Shapiro – wilks test and Q -Q plots. Since the groups do not follow the normal distribution Kruskal – Wallis test to test the statistical significance of post operative sensitivity among the groups. Mann – whitney U test was used to assess the post operative sensitivity among the control groups.

GROUPS INVOLVED:

CONTROL GROUPS:

GROUP 1: Total Etch (TE) Control Group

GROUP 2: Self Etch (SE) Control Group

TEST GROUPS:

GROUP 2: TE - GLUMA Application After Acid Etching

GROUP 3: TE - GLUMA Application Prior to Acid Etching

GROUP 5: SE - GLUMA Application Prior to Acid Etching

GROUP 6: SE - GLUMA Application After Acid Etching

NULL HYPOTHESIS:

The null hypothesis states that there is no statistically significant difference in post operative sensitivity on GLUMA application etching before or after total etching or self-etching followed by composite restoration of the carious teeth.

SAMPLE SIZE CALCULATION:

For this clinical trial, a sample size of 504 restorations was calculated to be sufficient for detecting statistical difference using G* power software (α probability error – 0.05 and effect size – 0.2).

TYPE OF ANALYSIS:

The type of trial is a Noninferiority trials. By definition a non – inferiority trial tests whether a new experimental treatment is not unacceptably less efficacious than an active control treatment already in use. With continuous improvements in health technologies, standard care, and clinical outcomes, the incremental benefits of newly developed treatments may be only marginal over existing treatments. (Hahn S. Understanding noninferiority trials. Korean journal of pediatrics. 2012 Nov 23;55(11):403.)

This test is a non - inferiority trial hence the six groups have GLUMA application before etching of a composite restoration which is not unacceptably less efficacious in reducing post operative sensitivity in composite restoration of a carious tooth.

PROCEDURE:

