A significance level of $p < 0.05$ was considered statistically significant throughout the analysis. In the present study, the Kruskal-Wallis test was used to compare six desensitizer groups at different time intervals (Pre-operative, 24 hours, 48 hours, and 1 week post-operatively) based on Visual Analog Scale (VAS) scores. Since each time point represents a distinct clinical endpoint, a separate Kruskal-Wallis test was conducted for each, yielding **individual p-values** corresponding to each time point. As the Kruskal-Wallis test does not permit aggregation of multiple outcomes into a single p-value, **a common p-value is not statistically appropriate**.

Ranks

	Desensitizer Group	N	Mean Rank	P Value ^a
Pre Op VAS	Total etch control	86	105.48	0.003
	Total etch Gluma prior to etching	94	141.70	
	Total etch Gluma after etching	86	116.12	
	Self etch control	82	142.30	
	Self etch Gluma prior to etching	80	106.20	
	Self etch Gluma after etching	76	147.55	
	Total	504		
Post Op sensitivity 24hr VAS	Total etch control	86	125.47	0.126
	Total etch Gluma prior to etching	94	122.94	
	Total etch Gluma after etching	86	117.62	
	Self etch control	82	136.49	

	Self etch Gluma prior to etching	80	125.30	
	Self etch Gluma after etching	76	132.62	
	Total	504		
Post Op sensitivity 48hr VAS	Total etch control	86	131.74	0.050
	Total etch Gluma prior to etching	94	127.98	
	Total etch Gluma after etching	86	123.48	
	Self etch control		132.76	
	Self etch Gluma prior to etching	80	114.36	
	Self etch Gluma after etching	76	128.18	
	Total	504		
Post Op sensitivity 1 week VAS	Total etch control	86	124.24	0.013
	Total etch Gluma prior to etching	94	130.96	
	Total etch Gluma after etching	86	124.38	
	Self etch control	82	129.76	
	Self etch Gluma prior to etching	80	115.00	
	Self etch Gluma after etching	76	134.53	
	Total	504		

p < 0.05 denotes statistically significant difference. All the values exhibit non – statistically significant difference. Statistical test applied *

Kruskal – Wallis test

Ranks

	Desensitizer Group	N	Mean Rank	*P Value
Pre Op VAS	Total etch control	86	36.83	0.012
	Self etch control	82	48.45	

	Total	168		
Post Op sensitivity 24hr VAS	Total etch control	86	40.67	0.337
	Self etch control	82	44.41	
	Total	168		

p< 0.05 denotes statistically significant difference. All the values exhibit non – statistically significant difference except the pre operative pain scores. Statistical test applied * Mann Whitney U test

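### Reported arm sizes (86/94/86/82/80/76) cannot be reconciled with blocks of six and 84 per arm, and the mean ranks imply 252 observations, not 504

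*Combined protocol and SAP*

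**What the plan says.** The Brief Summary, the Detailed Description and the SAP all state that "a sample size of 504 restorations was calculated to be sufficient for detecting statistical difference using G* power software", with "α probability error – 0.05" and "effect size – 0.2". Power is not given.

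On allocation, the Brief Summary and the Detailed Description say that "a block size of 6 (1, 2, 3, 4, 5, 6) was employed for equal enrolment" and that "After every 6th patient, the enrolment would continue on to the next block from 1". Patients are what is allocated; restorations are what the sample size counts. The Brief Summary heads its arm list "Arms (n=84 in each", and the Detailed Description repeats 84 against each arm.

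The six-group rank table under Procedure in the SAP gives other sizes: total etch control 86, total etch Gluma prior 94 (row "Total etch Gluma prior to etching"), total etch Gluma after 86, self etch control 82, self etch Gluma prior 80, self etch Gluma after 76. The total is printed as 504 at every time point. One cell, self etch control at 48 hours, is blank and is 82 by subtraction. The two-control table prints 86 + 82 = 168.

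The SAP's estimate is a 1-week mean difference of 0.18 between total etch Gluma after and self etch Gluma prior, with dispersion 0.1077 and a one-sided 95% lower limit of +0.003.

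There is no participant flow, no definition of the analysis set, no count of exclusions or replacements, and no number of restorations per patient.

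**The concern.** Blocks that hold one slot per arm and are filled in order keep the arms within one of each other throughout enrolment. A spread from 76 to 94 is not what that procedure produces, so either the description of the allocation or the reported numbers are wrong or incomplete. Every comparison in the SAP relies on arm membership and arm size. If restorations were analysed outside their allocated arm, or removed or replaced after allocation, the protection of randomisation is weakened. If the N column is wrong, the precision claimed for the estimate is wrong too.

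**Working it through.** **1. The planned total.** Inputs: 504, alpha 0.05, effect size 0.2, six arms. Assumptions, since the documents do not say: 0.2 is Cohen's f in a one-way ANOVA, and power is varied. From the noncentral F with noncentrality N × f², the smallest N is 327, 366, 418 and 501 for power 0.80, 0.85, 0.90 and 0.95. Rounded up to multiples of six these are 330, 366, 420 and 504. So 504 is reproduced if power was 0.95 (power at 504 is 0.952). On the same assumptions power at 252 is 0.67.

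**2. Block arithmetic.** 504 / 6 = 84 blocks, remainder 0, hence 84 per arm.

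| Arm | Planned | Printed N | Difference | Half of printed N | Half minus 42 |
|---|---|---|---|---|---|
| Total etch control | 84 | 86 | +2 | 43 | +1 |
| Total etch Gluma prior | 84 | 94 | +10 | 47 | +5 |
| Total etch Gluma after | 84 | 86 | +2 | 43 | +1 |
| Self etch control | 84 | 82 | -2 | 41 | -1 |
| Self etch Gluma prior | 84 | 80 | -4 | 40 | -2 |
| Self etch Gluma after | 84 | 76 | -8 | 38 | -4 |
| Total | 504 | 504 | 0 | 252 | 0 |

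The range is 94 - 76 = 18. The excess over plan is 2 + 10 + 2 = 14, equal to the deficit 2 + 4 + 8 = 14.

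**3. Over-enrolment followed by removal.** With one restoration per patient, an arm of 94 needs a 94th block. At least 93 × 6 + 1 = 559 would have been allocated (564 with complete blocks), and 55 to 60 later removed to leave exactly 504. No such count appears.

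**4. How many observations were ranked.** With or without ties, Σ(nᵢ × mean rankᵢ) / Σnᵢ = (N + 1)/2. For pre-operative VAS:

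(86×105.48 + 94×141.70 + 86×116.12 + 82×142.30 + 80×106.20 + 76×147.55) / 504 = 63755.8 / 504 = 126.50.

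The 24-hour, 48-hour and 1-week tables also give 126.50. Then N = 2 × 126.50 - 1 = 252; N = 504 would require 252.5. The two-control table gives (86×36.83 + 82×48.45)/168 = 42.50 pre-operatively and 42.50 at 24 hours, so N = 84, not 168. Every printed N is even, and the halves sum to 252.

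**5. Do the printed means fit 84?** If scores are whole numbers, a mean of 1.72 cannot come from 84 (144/84 = 1.71, 145/84 = 1.73), nor can 1.16 (97/84 = 1.15, 98/84 = 1.17). Both fit the halved sizes (81/47 = 1.72, 50/43 = 1.16) and their doubles.

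**6. Effect on the reported interval.** Inputs: 1-week SDs 0.27 (self etch Gluma prior) and 0.95 (total etch Gluma after), difference 0.18. SE = √(0.27²/n₁ + 0.95²/n₂); lower limit = 0.18 - 1.645 × SE.

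| n₁ / n₂ | SE | Lower limit |
|---|---|---|
| 84 / 84 (planned) | 0.1078 | +0.003 |
| 80 / 86 (printed) | 0.1068 | +0.004 |
| 40 / 43 (implied by ranks) | 0.1510 | -0.068 |

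The first row reproduces the SAP's 0.1077 and +0.003, so the published interval used 84 per arm, a size that neither compared arm has in the rank table.

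**The case against.** The strongest reply is that the plan allocates patients and counts restorations. If patients contributed varying numbers of teeth, patient-level blocks could be perfectly balanced while restoration counts differed, and every restoration would still be in its randomised arm. That stands as a possibility. It is undocumented, it would contradict the stated 84 per arm, and it would make observations within a patient dependent, which neither rank test allows for. A uniform two restorations per patient does not help: 252 patients in blocks of six give 42 per arm, not 43/47/43/41/40/38.

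It can also be said that tooth exclusions rested on pulp exposure or cavity standardisation, with preparation and radiographs checked by a supervisor blinded to allocation. That is fair. The documents do not say whether exclusion came before or after allocation, so selective replacement cannot be asserted.

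The sizes are unremarkable under unrestricted randomisation: Σ(nᵢ - 84)²/84 = 192/84 = 2.29 on 5 df, p = 0.81. They therefore conflict with blocking, but are not in themselves evidence of selection.

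A reader might cite the pre-operative difference (p = 0.003) as support. It is not: nothing links that imbalance to the departures in arm size, and the one pairwise pre-operative contrast reported (p = 0.012) is between the two controls, which are off plan by only +2 and -2.

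A reader might also infer from the 1-week ranks that only 0 to 6 scores per arm were non-zero, so that a few misplaced units could overturn a result. That takes the lowest mean rank, 115.00, as the tied rank of zero, which requires every self etch Gluma prior score to be zero. The SAP reports 0.08±0.27 for that arm, which fits 3 of 40 scoring 1 (mean 0.075, SD 0.267). The ranks alone give a minimum of 252 - 229 = 23 non-zero scores overall, not a maximum.

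**Conclusion.** The contradiction is established and must be resolved before the arm comparisons can be relied on. The printed sizes do not follow from consecutive blocks of six with 84 per arm, and the printed Ns are twice the numbers that were ranked. The imbalance is present on either count: a range of 18 on 504, or 9 on 252.

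The cause is not established. A reader might conclude that the sizes are impossible and that the analysed groups are therefore not the randomised groups. That goes too far: it needs 504 to be the number allocated, with one restoration each. The figure of at least 14 restorations outside their allocated arm rests on the same condition, with none removed. The documents cannot separate treatment outside the allocated arm, exclusion or replacement after allocation, a block list not followed as described, and a varying number of restorations per patient.

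For the reported interval, using the printed 80/86 changes nothing of substance (lower limit about +0.004). Using the 40/43 implied by the ranks moves the limit to about -0.07, so it no longer excludes zero. This takes the published SDs as correct and uses a normal quantile. Confidence is high in the mismatch, not in any explanation of it.

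**What to change.** - Match the dataset to the printed block sheets and establish each restoration's allocated arm.
- Replace the stated 84 per arm and the N column with the true numbers, and say whether 252 or 504 observations were analysed.
- Report by arm the patients and restorations allocated, excluded, replaced and analysed, and the number of restorations per patient. Say whether exclusions came before or after allocation.
- Define the analysis set. Make analysis by allocated arm primary, with as-treated analysis as a sensitivity analysis only.
- Recompute the rank tests, the dispersion and the confidence limit with the true arm sizes.
- If the sheets cannot be linked to the data, state that the comparison cannot be shown to be as randomised.

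The cost is record matching and a rerun of the analysis, with no new patients. It depends on the sheets still existing: the documents say they were printed, not that they were kept or can be linked to the data.

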5% of Glutaraldehyde component acts as a biological fixative, essentially coagulating proteins within the dentinal tubules and causing them to become blocked. This prevents the movement of fluid within the tubules, which is a primary cause of dentin hypersensitivity. 35% of HEMA is a hydrophilic monomer that also contributes to the occlusion of dentinal tubules. It enhances the penetration of the solution into the tubules and helps to further block the fluid flow. The mechanism of Gluma desensitizer is both the glutaraldehyde and HEMA work together to reduce the permeability of the dentin, thus minimizing the stimuli that trigger sensitivity.

In this clinical trial the numbers of arms were randomly assigned to six groups. Blinding helps to ensure that the results of the study are more reliable and less influenced by the subjective opinions or expectations of the participants or researchers. Hence in this clinical trial, single-blinding was done. The participants of the study were informed about the trial but were unaware of which treatment group they were allocated to. The clinician and researcher were aware of the groups and treatments given. This blinding was also done to minimize bias that could arise from the patient's expectations or perceptions about the treatment. In this clinical trial all the patients were allocated using Block randomization, a technique which is used to ensure balance in treatment group sizes throughout the trial. It works by dividing participants into individual blocks

and then randomly assigning treatments within each block, ensuring roughly equal numbers in each group within that block¹⁰. In this clinical trial, a block size of 6 (1, 2, 3, 4, 5, 6) was employed for equal enrolment. The prepared blocks were printed in sheets and patients who met the eligibility criteria were systematically assigned in a continuous fashion. After every 6th patient, the enrolment would continue on to the next block from 1.

Arm Title

Arm 1: Total Etch Control group (No desensitizer application) (n=84)

Arm 2: Total Etch Gluma prior to acid etchant usage (n=84)

Arm 3: Total Etch Gluma desensitizer application after acid etchant usage (n=84)

Arm 4: Self Etch Control group (No desensitizer application) (n=84)

Arm 5: Self Etch Gluma desensitizer application prior to etching (n=84)

Arm 6: Self Etch Gluma desensitizer application after self-etch adhesive usage (n=84)

Arm information and description:

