Acid Etchant: 37% Phosphoric acid (Prime Dental Products Pvt Ltd.,)

Bonding agent: Te-Econom Bond" is Ivoclar Vivadent,

Composite (Charisma Smart, Kulzer GmbH, Germany),

Gluma Desensitizer (Kulzer GmbH, Germany).

The agents used are **Self Etch groups (Arm 4- Arm 6)** are,

Bonding agent: 3M ESPE Single Bond Universal Adhesive, Germany

Composite (Charisma Smart, Kulzer GmbH, Germany),

Gluma Desensitizer (Kulzer GmbH, Germany).

Intervention Type: Drug used in this clinical trial is Gluma Desensitizer (Kulzer GmbH, a German company).

Description: Caries excavation was done using diamond burs (Mani Co., Tochigi, Japan) with water coolant. Extent of caries excavation was done until sound hard or firm discolored or non-discolored dentin was achieved. Extent of caries excavation was assessed by an Experienced Post Graduate Supervisor (EPGS) blinded to treatment allocation group. Those teeth with width of the cavity preparation were no more than 1/3rd of the inter-cuspal width were included. Radiographs (Durr PSP Sensor, Durr, Germany) are taken to assess the depth of the preparation and Remaining Dentin Thickness (RDT). Two RDT measurements from mesial and distal pulp horn to floor of the preparation were calculated. Mean RDT was derived from the two readings. Preparation extending beyond the middle third of the dentin or with pulp exposure is excluded from the study. Radiograph assessment was done by EPGS. Teeth were excluded from the study if

they had pulp exposure or a prepared cavity that did not

meet standardization requirements.

Intervention description for Arm 1 (**Total Etch Control group (No desensitizer application)**) after cavity preparation, Total-etch adhesive was applied in the following way: 37% Phosphoric acid (Prime

Dental Products Pvt Ltd.,) was applied for 20 s on the prepared cavity. The acid was then washed by air and water pressure through a triple syringe for 20s. The surface was lightly air-dried. Then two coats of primer-bond solution (Te-Econom Bond, Ivoclar Vivadent) were applied by scrubbing with a micro brush, for 20 s per coat. When the surface became shiny, it was light-cured for 20s (Woodpecker LED, Guilin, China). After curing the adhesives, the light-cured nano-composite (Charisma Smart, Kulzer GmbH, Germany) was used for the restoration which was applied in increments (1–2 mm thick) by layering technique to reduce polymerization shrinkage.

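### Teeth are kept or dropped only after the cavity is cut, the timing of allocation relative to that step is not stated, and nothing described keeps the arm from the operator

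*Combined protocol and SAP*

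**What the plan says.** Tooth-level eligibility is described in Materials and Methodology and again in the Detailed Description:

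- Width: "Those teeth with width of the cavity preparation were no more than 1/3rd of the inter-cuspal width were included".
- Depth (Detailed Description only): "Preparation extending beyond the middle third of the dentin or with pulp exposure is excluded from the study".
- General ground, in both places: "Teeth were excluded from the study if they had pulp exposure or a prepared cavity that did not meet standardization requirements".

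On allocation, Sample Size, Blinding and Randomization says "The prepared blocks were printed in sheets and patients who met the eligibility criteria were systematically assigned in a continuous fashion", and that "a block size of 6 (1, 2, 3, 4, 5, 6) was employed for equal enrolment". No concealment is described, and the documents do not say who held the sheets.

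On who knew the arm, the same section says "The clinician and researcher were aware of the groups and treatments given". The Detailed Description adds "Extent of caries excavation was assessed by an Experienced Post Graduate Supervisor (EPGS) blinded to treatment allocation group". The radiographs are read by the same supervisor.

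The documents do not state the order of allocation and cavity acceptance, who judges width, exposure or standardization, or who takes the decision to exclude. They give no count of exclusions by arm.

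**The concern.** Every tooth-level criterion is a property of the finished preparation, so a tooth's place in the trial is settled only after an operator who knows the groups has cut the cavity. If the arm was already assigned, teeth could leave after assignment in a way that depends on the arm. If it was not, an operator who can see or work out the next entry on the sheet could let that influence whether a tooth enters.

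In both cases the retained teeth in the six arms could differ in depth or width for reasons other than chance. Teeth excluded after assignment would have no recorded outcome, so no later analysis could bring them back. Remaining dentin thickness was measured, but the results do not report it by arm, so a reader cannot check whether the retained teeth were comparable.

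**Working it through.** **1. Order of steps, from the text.** Two features suggest that allocation came first. The supervisor who checks the excavation is called blinded to an allocation group, which fits most naturally if an allocation exists by then. Also, it is patients who are assigned, while it is teeth that are later excluded. One feature points the other way: those assigned are patients who had met the eligibility criteria, and width and depth are written as such criteria. The text does not settle the order.

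**2. Does the order matter?** If allocation came first, the operator knows the current arm when the cavity is cut. If it came second, the next arm can be read from an open printed sheet. Even without seeing the sheet, anyone who knows the last five assignments in a fixed block of six knows the sixth. The exposure exists under both orders and differs only in kind: loss after assignment, or selection at entry.

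**3. The planned sample size.** The plan gives 504 restorations, alpha 0.05 and effect size 0.2, without power. A one-way ANOVA with six groups and f = 0.2 (noncentrality 504 × 0.04 = 20.16) needs 330, 366, 420 or 504 in total for power 0.80, 0.85, 0.90 or 0.95. So 504 is reproduced at an assumed power of 0.95 with nothing added for exclusions. It also equals 420 × 1.20, which is power 0.90 plus 20%. The documents mention no allowance, so this figure does not show whether exclusions were expected.

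**4. Analysed arm sizes (Ranks table).** These are 86, 94, 86, 82, 80 and 76, total 504, against 84 planned per arm.

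- With one restoration per patient, blocks of six keep arms within 1 of each other. The observed range is 94 − 76 = 18.
- If later exclusion were the only cause, at least 94 + 5 × 93 = 559 were assigned and 559 − 504 = 55 lost (55/559 = 9.8%).
- With complete blocks, 6 × 94 = 564 were assigned and 60 lost (10.6%). By arm the losses would be 8, 0, 8, 12, 14 and 18, or 0% to 19% of 94.
- The counts themselves need reconciling. The mean ranks, weighted by N, average 126.5 = (252 + 1)/2, whereas 504 observations would give 252.5. On half-size arms (43, 47, 43, 41, 40, 38), the same logic gives at least 47 + 5 × 46 = 277 assigned and 25 lost (9.0%).

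**5. Possible size of a shift at 24 h.** Suppose an arm would average 0.50 (assumed; reported 24 h arm means run from 0.20 to 0.66). A fraction f of its teeth, which would have averaged VAS m (assumed), is dropped, and the comparator loses none. The retained mean is (0.50 − f·m)/(1 − f).

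| m | f = 5% | f = 10% |
|---|---|---|
| 1 | 0.45/0.95 = 0.474, shift 0.03 | 0.40/0.90 = 0.444, shift 0.06 |
| 2 | 0.40/0.95 = 0.421, shift 0.08 | 0.30/0.90 = 0.333, shift 0.17 |
| 3 | 0.35/0.95 = 0.368, shift 0.13 | 0.20/0.90 = 0.222, shift 0.28 |

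Reported 24 h differences between each Gluma arm and the control with the same adhesive:

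- Total etch, Gluma before: 0.49 − 0.37 = +0.12
- Total etch, Gluma after: 0.28 − 0.37 = −0.09
- Self etch, Gluma before: 0.20 − 0.66 = −0.46
- Self etch, Gluma after: 0.61 − 0.66 = −0.05

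A shift of 0.03 is smaller than all four in absolute size. A shift of 0.08 exceeds one, and 0.13 exceeds three. None of the tabulated shifts reaches 0.46.

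**The case against.** The strongest reply is that the plain wording already answers the point: "patients who met the eligibility criteria were systematically assigned in a continuous fashion". If prepared width and depth are among those criteria, they were met before assignment, and the arms as described diverge only after preparation. The same supervisor is also called blinded at the one-week assessment, so the word may be a standing label for the role and say nothing about timing. This reply stands as far as it goes: a reader might infer that allocation preceded preparation, and the documents do not establish it. It does not clear the design, because the next arm could still be foreseen.

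A second reply is that safeguards exist. The excavation end point is tied to the state of the dentin and checked by that supervisor, who also reads the radiographs. Width and depth have stated limits, and the standardization ground may only summarise them. This also stands in part. It would be wrong to say that the supervisor's blinding offers no protection, since it reduces the risk for depth. It does not cover width, exposure or the exclusion decision, for which no one is named, and the operator still cuts the cavity.

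A third reply concerns the evidence. A reader might take the unequal arms, or the pre-operative VAS difference (p = 0.003), as a sign that teeth were dropped selectively. The documents do not support that. The arm sizes would also fit simple randomisation (chi-square 2.29 on 5 df, p = 0.81), several restorations per patient, departures from the list, or errors in the counts. The pre-operative difference is compatible with selection but does not prove it.

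**Conclusion.** The point holds in a limited form. Eligibility is settled on the cut cavity, the order of allocation and acceptance is not stated, and no described safeguard keeps the current or next arm from an operator who is aware of the groups. This is an avoidable opening for bias, not a demonstration that bias occurred. It would go too far to say that randomisation was in fact undone, because no exclusion after assignment is documented.

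The size is unknown. At 5% one-sided loss the shift is 0.03 to 0.13 for assumed VAS 1 to 3 among the lost teeth, against reported differences of 0.05 to 0.46. It would be smaller if the comparator lost similar teeth. The VAS values, the base mean of 0.50 and the loss fractions are assumptions with no source in the documents. Confidence is medium, because the timing is inferred.

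**What to change.** For any further enrolment, keep the arm concealed from the operator until the supervisor has accepted the prepared cavity. Tie the standardization ground to the width and depth limits already written in Materials and Methodology and the Detailed Description. The arms are described identically up to the finished cavity, so no treatment step changes. The arm is simply opened later in the same visit.

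For patients already treated, state when the arm was in fact revealed and who decided exclusion, and whether that person was blinded. Report by arm the teeth assigned, excluded after assignment (with reason) and analysed. If any were excluded after assignment, describe the comparison as one of retained teeth, not of all randomised teeth. The report should not say that the arm was opened after sign-off unless that is what happened. If no tooth was excluded after assignment, one sentence saying so answers that part; the timing of allocation still needs stating.

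The cost is a wording change and a table of counts. The counts depend on records of assignment and exclusion having been kept, which the documents do not confirm. If they were not kept, that should be reported as a limitation.
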